8.4. MULTI-CENTER STUDIES

There is no plan to include study center in the primary analysis because the MMRM will already include a random effect for patient. A model with random patient effects nested within study center would be unwieldy due to expected small numbers of patients per study center and large number of centers.

However, to satisfy ICH guidance (E9 Section 3.2), the difference between treatment means in the change from baseline with respect to the weekly mean of the daily 24-hour pain intensity for the index joint for each center will be plotted by week (observed data only). Only centers with at least 2 patients per treatment group will be included in this plot.

8.5. MULTIPLE COMPARISONS / MULTICLARITY

One primary efficacy endpoint has been specified in the protocol and the study has been powered sufficiently to show statistical significance in this endpoint. However, as this study is a Phase 2 study, there will be no adjustment for multiplicity for secondary endpoints. The results for the primary efficacy analysis will be the key result to aid planning of future Phase 3 studies. Results from other endpoints may be used to aid the generation of future hypothesis to be explored and/or warrant inclusion of such endpoints in future studies.

8.6. EXAMINATION OF SUBGROUPS

Summaries relating to the Pain Intensity and WOMAC endpoints will be presented by location of the primary OA joint.

9. STUDY POPULATION CHARACTERISTICS

Unless specified otherwise, all summaries of study population characteristics will be summarized for the FAP. Since the SAF and FAP are equivalent populations, an additional summary table for patients in the SAP will only be produced if any patients are mis-randomized.

9.1. SUBJECT DISPOSITION

A complete accounting of patient participation in the study will display the number of patients that were enrolled (i.e. signed informed consent) and the number and percentage of patients that were:

- Screen failures (Enrolled population)
- Randomized (Enrolled population)
- Randomized following re-screening (Enrolled population)
- Dosed with study drug (Enrolled population)
- Included in each population (FAP, SAF, PP)
- Completed the 8-week treatment with study drug
- Discontinued the study drug early with reasons
- Completed the follow-up visit

In addition, the number and percentage of patients completing each week of the Titration to Effect Period and completing the Maintenance Treatment periods, as well as the assigned doses across each week/period will be summarized.

Listings including the patient disposition, status with respect to inclusion and exclusion criteria, and population eligibility will be presented.

9.2. PROTOCOL DEVIATIONS

Major protocol deviations and deviations that may affect the analysis of efficacy will be summarized for all patients. All protocol deviations will be listed, and sorted by patient number and date of deviation (if available). This by-patient listing will identify whether a specific protocol deviation is major or minor, and whether it is considered to potentially affect the analysis of efficacy.

9.3. DEMOGRAPHICS AND BASELINE CHARACTERISTICS

Demographic and baseline characteristics will be summarized based on the information provided during the screening visit. The demographic characteristics to be summarized are

listed below with details of whether they will be summarized as a categorical (with categories if not direct from the eCRF) or continuous variable:

- Age at study entry – continuous
- Age at study entry – categorical
 - 25 to 44; 45 to 64; 65 to 74; 75+
- Gender – categorical
- Race – categorical
- Ethnicity - categorical
- Weight (kg) – continuous
- Height (cm) – continuous
- Body Mass Index (BMI) (kg/m²) – continuous
- Duration of time with OA – continuous
- Location of primary OA - categorical

Age at study entry will be calculated as (date the informed consent was signed – date of birth) / 365.25 rounded down to the nearest integer.

The supportive data for the summary of demographic and baseline characteristics will be listed, and sorted by patient number.

9.4. MEDICAL HISTORY

The medical history reported on the eCRF will be coded to Medical Dictionary for Regulatory Activities Terminology (MedDRA) terminology. Coded medical history terms will be summarized by SOC and Preferred Term. Medical history data will be listed including the verbatim investigator description of the relevant history, the coded terms, the start/stop dates, and whether the history is ongoing, if not stop date is provided.

A separate listing will be created with all the distinct levels of SOC, Preferred Terms and the verbatim investigator description reported in the study. Sorting will be alphabetically by SOC, Preferred Term and then verbatim description.

9.5. DOSING AND EXTENT OF EXPOSURE

Treatment compliance (%) will be calculated as follows:

$100 * \frac{\text{Number of doses actually taken}}{\text{Expected number of doses to have been taken}}$

Expected number of doses to have been taken

During the Titration to Effect and Maintenance Treatment periods as well as over the study, it is most likely the first dose will be a PM dose (following a clinic visit) and the last dose will be an AM dose (prior to a clinic visit). Therefore, the expected number of doses over a particular period will be calculated as [end date – start date] * 2.

The number of doses actually taken will be compared to the expected number of doses to derive the number of missed doses. There will be monitoring by the clinic staff to ensure that the diary dosing coincides with the drug accountability at each visit.

The number of missed doses (0, 1, ≥ 2) and treatment compliance (continuous and as categories <80%, 80% to 110%, >110%) will be summarized for the Titration to Effect, Maintenance Treatment and overall study period. Additionally, the length of exposure to study drug (continuous and as overlapping categories: any exposure, ≥ 1 week, ≥ 2 weeks, ≥ 4 weeks, ≥ 8 weeks), maximum titration level (1mg, 2.5mg and 5mg) and average dose taken over the study will be summarized.

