8.7 Dosing Regimen

Study medication will be taken BID. It is recommended that the medication be taken 2 hours before a meal or about 4 hours after a meal. The first dose should be taken at mid-morning (9:30-10 am) assuming breakfast is between 6 and 7 am and lunch is after 12 pm and the second dose should be taken just before going to bed at night, 4 hours post the last meal.

Study medication should be taken with a full glass of water (250 mL).

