8.10 Treatment Compliance

All patients will receive the first dose of study medication at the study site under the surveillance of appropriate study personnel. The dosing time will be recorded in the patient's eCRF.

A visit window of plus or minus one day will be allowed.

Treatment compliance with study medication regimens will be assessed by study personnel via tablet counts of returned medication and by questioning the patient, if necessary, at every posttreatment visit.

Patients will be considered noncompliant if they miss more than one dose during the Titration-to-Effect period and will be discontinued from the study.

Patients will be considered noncompliant if their overall study drug use is not within 80% to 110% (inclusive) of the expected drug use during the Maintenance Treatment period. A patient who is not compliant (took < 80% or > 110% of study medication) will be discontinued from the study.

In addition, for each 7-day administration period, patients will be asked to record their daily intake of study medication on a diary card. These diaries will be reviewed by study personnel at each visit and will be collected as source documents. Information from the patient diary will be transcribed onto the appropriate eCRF pages for documentation of patient compliance with study medication.

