9.1.2 Baseline (Visit 2)

Baseline is defined as Day 1 (Visit 2). The following procedures will be performed at baseline:

- 1. Obtain a blood sample for serum sodium (sodium level must be ≤ 143 mmol/L) prior to dispensing study medication). If sodium level is > 143 mmol/L, then the patient can be retested in approximately 1 hour after being given a glass of water to drink.
- 2. Perform urine pregnancy test for female patients of childbearing potential.
- 3. Record any changes in prior and current therapies (e.g., prescription and non-prescription medications).
- 4. Assess vital signs.
- 5. Assess and record any AEs that have occurred since the last evaluation. Those will be recorded as medical history.
- 6. Perform drug accountability and, if necessary, counsel on compliance.
- 7. Review NRS data in the patient diary (Day -7 to Day -1) to calculate the Baseline NRS score and determine study eligibility. (The patient must have 4 pain scores at the index joint ≥ 5 for 4 or more of the last 7 days, with 2 consecutive days ≥ 5 immediately prior to randomization).
- 8. Review inclusion/exclusion criteria.
- 9. If patient is eligible:
 - a. Assign the next patient number.
 - b. Obtain blood samples for clinical laboratory evaluations including serum sodium.
 - c. Have the patient complete the WOMAC.
 - d. Dispense study medication and administer the first dose.
 - e. Instruct patient on the use of rescue medication and fluid replacement.
 - f. Review the PRO assessments and the recording of information in the patient diary.
 - g. Schedule Visit 3 (Day 8) and instruct the patient to discontinue acetaminophen at least 12 hours prior to the clinic visit.

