11.7 Study Drug Accountability

A data listing of the study drug dispensed and returned will be provided.

Patients will be considered noncompliant if they miss 2 or more doses during the Titration-to-Effect period.

Patients will be considered noncompliant if their overall study drug use is not within 80% to 110% (inclusive) of the expected drug use during the Maintenance Treatment period.

The expected number of tablets to be taken will be calculated based on the duration of treatment. The count and percentage of patients compliant with study drug will be summarized by treatment group (CR845 vs. placebo).

The number of patients who titrated to Level 1 (CR845 1 mg or matching placebo), Level 2 (CR845 2.5 mg or matching placebo) or Level 3 (CR845 5 mg or matching placebo) will be summarized. In addition, the average dose of each patient during the study will be calculated and presented for each treatment group.

The number and percentage of patients exposed to double-blind study drug for overlapping time intervals (e.g., any exposure, ≥ 1 week, ≥ 2 weeks, ≥ 4 weeks, ≥ 8 weeks) will be calculated by treatment group. Descriptive statistics (mean, standard deviation (SD), median, minimum, maximum) will be provided to summarize the length of exposure (in days) to each treatment.

Dosing details and any deviations from the planned dose will be listed.

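### SAP 9.5 assumes an evening first dose, although the first dose is given at the Day 1 clinic visit; where that is a morning dose, titration and overall missed doses can be understated by one

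*SAP*

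**What the plan says.** SAP 9.5 defines compliance as doses taken divided by doses expected. One assumption covers three periods, "During the Titration to Effect and Maintenance Treatment periods as well as over the study": the SAP holds that "it is most likely the first dose will be a PM dose (following a clinic visit") and that "the last dose will be an AM dose (prior to a clinic visit"). It concludes that "the expected number of doses over a particular period will be calculated as [end date – start date] * 2". Missed doses come from comparing doses taken with doses expected, and are tabulated as 0, 1 and 2 or more for titration, maintenance and the whole study.

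The protocol describes Day 1 differently. Section 8.10 states: "All patients will receive the first dose of study medication at the study site under the surveillance of appropriate study personnel". The Visit 2 procedures in section 9.1.2 say: "Dispense study medication and administer the first dose". Footnote 7 of the SAP's own Table 1 also has the first dose taken at the clinic. On daily timing, Protocol 8.7 says: "The first dose should be taken at mid-morning (9:30-10 am"), with the second dose at bedtime.

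The limit that makes the count matter is in Protocol 11.7: "Patients will be considered noncompliant if they miss 2 or more doses during the Titration-to-Effect period". Protocol 8.10 words the same limit as more than one missed dose.

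**The concern.** The date-difference formula is exact only when a period opens with an evening dose and closes with a morning dose. That fits maintenance, which opens after the Day 29 visit. It does not obviously fit a period that opens with a supervised dose at the Day 1 visit. If that dose is the first of the day's two, a bedtime dose still follows on Day 1, and the formula leaves one dose out of the expected count.

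One dose in 56 or 112 hardly changes a percentage. The missed-dose table, however, is cut at 0, 1 and 2 or more, and its last boundary is the protocol's titration limit for non-compliance. A shift of one moves patients across that boundary, always towards better apparent adherence. A patient withdrawn on site for missing two titration doses could then appear in the missed-dose table as having missed one.

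**Working it through.** **Inputs**
- Formula: (end date - start date) × 2 (SAP 9.5).
- Bounding visits: Days 1, 29 and 57 (Protocol 9.1).
- Two daily doses, mid-morning and bedtime (Protocol 8.7), called AM and PM here.
- Missed doses taken as expected minus taken (SAP 9.5 says the two are compared).

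**Step 1: the SAP's result on its own premise.** The SAP prints no totals, so the formula is applied to the planned visit days.
- Titration: (29 - 1) × 2 = 56.
- Maintenance: (57 - 29) × 2 = 56.
- Overall: (57 - 1) × 2 = 112.

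Counting slots from a PM first dose to an AM last dose also gives 56, 56 and 112. The formula is correct for the premise stated.

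**Step 2: all first/last combinations, by counting slots.**

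| First dose | Last dose | Titration, Day 1–29 (formula 56) | Overall, Day 1–57 (formula 112) | Shortfall |
|---|---|---|---|---|
| PM | AM | 56 | 112 | 0 |
| AM | AM | 57 | 113 | 1 |
| PM | PM | 57 | 113 | 1 |
| AM | PM | 58 | 114 | 2 |

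The row that combines a morning clinic dose on Day 1 with the SAP's own AM last dose is AM/AM: 28 × 2 + 1 = 57 and 56 × 2 + 1 = 113. Maintenance from Day 29 PM to Day 57 AM is 56, as the formula says.

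**Step 3: effect on a titration patient in the AM/AM case.**

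| Truly missed | Taken | SAP missed (56 - taken) | SAP compliance | Compliance on 57 |
|---|---|---|---|---|
| 0 | 57 | -1 | 101.8% | 100.0% |
| 1 | 56 | 0 | 100.0% | 98.2% |
| 2 | 55 | 1 | 98.2% | 96.5% |
| 3 | 54 | 2 | 96.4% | 94.7% |

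The percentage moves by less than 2 points, so the 80% to 110% bands are barely affected. The count moves by one everywhere. The -1 has no category in the table, and two true misses fall below the cut-off.

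**Step 4: the undefined end date.** SAP 9.5 does not say which date closes a period. SAP 4.1 labels titration as Days 1–28. If the end date were Day 28 with a PM last dose and an AM first dose, 56 doses would be due against (28 - 1) × 2 = 54, a shortfall of two.

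**The case against.** The strongest reply is that no section states clinic visit times, so a shortfall of one is not established for any given patient. If the Day 1 clinic dose counts as that day's PM dose, the formula is exact. It is also exact if visits precede the mid-morning dose at both ends: the patient then takes Day 1 AM to Day 28 PM, which is 56 doses, and with the end date left at Day 29 the formula returns 56. Protocol 8.7 gives a recommended daily routine and does not time the Day 1 dose, which follows sodium testing, eligibility review and other procedures. The formula also matches the nominal duration: 56 days in Protocol 6.3 × 2 = 112, and 28 titration days × 2 = 56. The SAP itself calls its premise only most likely.

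Most of this stands, and it makes the undercount conditional. It does not remove the conflict over where the first dose is taken. The second exact case also requires that the Day 29 morning dose was not taken before the visit, contrary to the SAP's own last-dose assumption.

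A reader might go further and infer a proportion of patients misclassified. With 57 slots and independent misses, the probability of exactly two is 1596 × p² × (1 - p)^55, which is 0.092, 0.210 or 0.269 for p = 0.01, 0.02 or 0.03. The documents do not support using these as shares of the trial. They give no miss rate, and the calculation needs every patient to start in the morning and run through all 57 slots. It also ignores the rule in Protocol 8.10 that patients missing more than one titration dose are discontinued.

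It is also fair to say that little rests on the formula. On-site compliance uses tablet counts and questioning (Protocol 8.10), per-protocol exclusions are settled at the blinded data review (SAP 7.2.2 and 7.4), and no efficacy analysis uses it.

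**Conclusion.** The conflict is real: for titration and the whole study, the first-dose premise of SAP 9.5 disagrees with Protocol 8.10 and 9.1.2 and with footnote 7 of SAP Table 1. The numerical error is conditional. It is one dose (57 against 56, and 113 against 112) when the Day 1 clinic dose is the morning dose and the last dose is the morning dose of the closing visit. In that case two missed titration doses are shown as one, and full adherence is shown as -1.

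It would be wrong to read this as an undercount in every patient, since the formula holds for maintenance and, under the timings described above, for titration. The number affected cannot be derived from the documents. The consequence is confined to the descriptive missed-dose and compliance tables, including the count of compliant patients planned in Protocol 11.7. This is a minor but worthwhile correction.

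**What to change.** Reconcile SAP 9.5 with Protocol 8.10 and 9.1.2 and with footnote 7 of SAP Table 1. Define the start dose and end dose of each period, including for patients who stop early. Then replace the blanket formula with a per-patient count of AM/PM dose slots from the recorded first dose to the recorded last scheduled dose:

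- expected doses = (end date - start date) × 2, plus
- 0 if the first is PM and the last is AM;
- 1 if the first is AM and the last is AM;
- 1 if the first is PM and the last is PM;
- 2 if the first is AM and the last is PM.

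Use this count for both missed doses and percent compliance. All four cases are needed, because afternoon visits and early stops can produce any of them.

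The cost is one derivation rule and its programming. The data are already collected: the time of the first dose goes into the eCRF (Protocol 8.10), and AM/PM dosing is in the diary from Day 1 (SAP 4.1). No study procedure changes.

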9.6. PRIOR AND CONCOMITANT MEDICATION AND THERAPIES

Prior medications are defined as medications taken at any time during the 30 days prior to Screening until the time of dosing on Day 1, whether continuing or not. Any changes to prior medications (dose, regimen, etc.) during the study will be considered a new *Concomitant Medication*.

Concomitant medications are defined as any medications taken following the administration of the first dose of study drug on Day 1 through the end of the study (i.e., at the Follow-up Visit). These will be categorized into two groups, 1) During treatment with study drug and 2) Following end of treatment with study drug.

Whether a medication is prior, concomitant or both will be assessed by comparing the start date of the medication to the date of the first dose. If the medication start and/or end date is fully missing or sufficiently partially missing such that it cannot be determined whether it was taken prior to the first dose of study drug, then the medication will be considered concomitant. Similarly, if the medication start and/or end date is fully missing or sufficiently partially missing such that it cannot be determined whether it was taken following the last dose of study drug then it will be classed as being concomitant during treatment with study drug.

Prior and Concomitant medications (during and after treatment) will be coded using the Anatomical-Therapeutic-Chemical (ATC) classification text from the World Health Organization Drug Dictionary (WHO DD) and summarized separately. The number and percentage of patients taking a medication will be displayed by ATC Class 1 and Preferred Term. Patients will only be counted one time in each unique ATC Class 1 and Preferred Term.

All prior and concomitant medications will be listed and will include both the medication name as reported by the investigator as well as the coded information.

A separate listing will be created with all the distinct levels of ATC Class 1, Preferred Terms and the verbatim investigator description reported in the study. Sorting will be by ATC Class 1, Preferred Term and then verbatim description.

10. EFFICACY ANALYSES

All efficacy analyses will be conducted on the FAP and PP population if necessary (see Section 8).

In addition to the statistical analyses described in the sections below, descriptive summaries (as per Section 8) and data listings sorted by unique patient number will be presented for all efficacy variables.

10.1. PRIMARY EFFICACY VARIABLE

To account for the interim unblinded sample size re-assessment, the analyses relating to the primary efficacy variable will employ weighted test statistics as proposed by Cui, Hung and Wang in order to maintain the 5% two-sided type 1 error rate. As there is no potential for early stopping of the study, no adjustments need to be made to the significance levels for the combined final analysis. The primary analysis and sensitivity analyses described in this section will be performed on each stage (pre and post interim patients) separately and test statistics (t_1 and t_2) from each stage will be combined to obtain the CHW Z statistic as follows:

$Z_{CHW} = \sqrt{0.5} t_1 + \sqrt{0.5} t_2$ from which the two-sided p-value will be obtained using the normal distribution.

Point estimates and 95% CI will be obtained using methodology suggested by Hung and Lawrence²:

Point estimate:

$$\hat{\delta} = \frac{t_1 \hat{\delta}^{(1)} + \sqrt{1-t_1} \sqrt{t^* - t_1} \hat{\delta}^{(2)}}{t_1 + \sqrt{1-t_1} \sqrt{t^* - t_1}}$$

where

$t_1 = 0.5$

$t^* = (\text{Re-estimated total sample size})/405$

$\hat{\delta}^{(1)}$ = Least square mean difference from stage 1 analysis

$\hat{\delta}^{(2)}$ = Least square mean difference from stage 2 analysis

$$95\% \text{ CI} = \hat{\delta} \pm \left(\frac{\hat{\delta}}{Z_{CHW}} * 1.96 \right)$$

The primary analysis and each sensitivity analysis will also be performed using the full combined dataset with no CHW adjustment. Presentation of results will start with these analyses (additionally including the CHW results) and then follow with the results of the analysis from each individual stage.

The primary efficacy variable will be analyzed using a mixed effect model with repeated measures (MMRM). The model will contain treatment (placebo vs CR845), treatment-by-week interaction as fixed effects, baseline value and OA joint (hip vs knee) as covariates, and patient as a random effect.

The treatment difference between CR845 (across all doses) and placebo at Week 8 (the primary efficacy endpoint) will be estimated as the simple contrast in the treatment effect. The 2-sided 95% confidence interval (CI), based on the difference in the least squares (LS) means between the 2 treatment groups (CR845 vs placebo) will be presented. The LS means (and 95% CI) will be additionally be presented for each treatment for each week.

The MMRM model will be implemented using SAS PROC MIXED. A restricted maximum likelihood (REML) will be used. The Kenward-Roger³ approximation will be used to estimate the denominator degrees of freedom and adjust standard errors. An appropriate covariance matrix will be used to model the within patient errors until there are no convergence issues in the following order: 1) unstructured, 2) Toeplitz, 3) autoregressive [1], 4) compound symmetry, 5) variance components. For analyses of multiple imputed datasets, this selection will continue until analyses for all imputations converge.

The treatment of missing data will be addressed using pattern mixture model methodology. Within each treatment, 4 data patterns will be defined as follows:

- Pattern 1: will include patients who completed treatment on study drug
- Pattern 2: will include patients who discontinue treatment early due to AEs
- Pattern 3: will include patients who discontinue treatment early due to lack of therapeutic efficacy (LOTE)
- Pattern 4: will include patients who discontinue treatment early due to reasons other than AE event or LOTE.

The pattern mixture model methodology will be implemented using SAS procedures MI and MIANALYZE. Specifically, the following steps will be followed:

- Intermittent missing data will first be imputed using the Markov Chain Monte Carlo (MCMC) method implemented with the SAS MI procedure, which is appropriate for non-monotonic missing data.
- Data for patients who discontinues early will be multiply imputed as follows:
 - If the patient discontinues due to AE (pattern 2) or LOTE (pattern 3), then missing data will be assumed to follow a distribution similar to the baseline values observed in the patient's randomized treatment.
 - If the patient discontinues due to reasons other than AE or LOTE (pattern 4), at each time point, missing data will be assumed to follow a distribution similar to scores for patients that are still in the study and randomized to the same treatment group.
- Results of the MMRM on the multiply imputed data will be summarized using the SAS MIANALYZE procedure using Rubin's rule.

A detailed plan of the above procedure is included as an attachment in Section 16.1.

Three sensitivity analyses (described below) will be conducted to assess the impact of the treatment of missing data on the study results. These sensitivity analyses may not necessarily reach statistical significance at the 5% level. However, a consistency of treatment effect (similar estimate of CR845 mean relative to placebo) is expected across the primary and all sensitivity analyses.

The MMRM analysis will be applied using observed data only to provide a reference in addition to the following sensitivity analyses:

Sensitivity analysis 1 (Multiple Imputation Missing at Random⁴)

This sensitivity analysis assumes that patients with missing data follow the same trajectory as other patients in their respective treatment arm that have complete data.

- Intermittent missing data will first be imputed using the MCMC method implemented with the SAS MI procedure, which is appropriate for non-monotonic missing data.
- Data missing after patients discontinue treatment early will then be multiply imputed with the SAS MI procedure using a method appropriate for monotone missingness (e.g., regression statement). At each time point, missing data will be assumed to follow a distribution similar to scores for patients who are still in the study and randomized to the same treatment group.
- Results of the MMRM on the multiply imputed data sets will be summarized by the SAS MIANALYZE procedure.

Sensitivity analysis 2 (Multiple Imputation, Missing not at random, placebo-based imputation⁴)

This sensitivity analysis assumes that patients in the active treatment group who discontinue early will have the same evolution, after treatment is stopped, as patients in the placebo group (who are not exposed to treatment by definition). Patients who discontinue treatment early in the placebo group are assumed to behave as the placebo patients that remain in the study.

- Intermittent missing data will first be imputed using the MCMC method implemented with the SAS MI procedure, which is appropriate for non-monotonic missing data.
- Data missing after patients discontinue treatment early will be multiply imputed using multiple calls of the SAS MI procedure. At each time point, missing data will be imputed using data from patients in the placebo group that have complete data at that time.
- Results of the MMRM on the multiply imputed data sets will be summarized by the SAS MIANALYZE procedure.

Sensitivity analysis 3 (Single Imputation, MNAR, Hybrid BOCF /LOCF):

This sensitivity analysis makes different assumptions about the pain trajectory of patients who discontinue study drug early depending on the reason for discontinuation. For patients who

discontinue due to AE, Baseline Observation Carried Forward (BOCF) will be used. For patients who discontinue due to reasons other than AE, Last Observation Carried Forward (LOCF) will be used. It is plausible that patients who discontinue due to LOTE experience worsening pain scores after randomization; in this case, their last observed pain scores would be higher (worse) than their baseline pain scores. This sensitivity analysis assumes that missing data for these patients is similar to observed pain scores for patients who discontinue due to LOTE but are still in the study.

